4.3. Partner Self-Testing Arm

3.4.4.1 Baseline Visit for Index Client

A random sample of individuals will be screened and consented as they exit their ART visit. This will include ART clients who report having a sexual partner with an unknown HIV status. After written informed consent has been obtained, study staff will collect basic socio-demographics (including age, gender, marital status, and number of partners), HIV characteristics (date of HIV diagnosis, whether on ART and date started), and the number of eligible sexual partners they plan to give self-test kits.

The study staff will counsel the index client on how to administer an HIV self-test and will provide one self-test kit for each sexual partner within the last 12 months with unknown status (or HIV-negative more than 6 months ago) who lives within the catchment area of the facility and for whom the index client is willing to provide the test kit (up to three sexual partners). Index clients will also be given self-test kits for themselves if they wish to use them to complete couples counseling. All HIV self-test kits will be labeled with a unique ID linked to the index client participant. The ID will also be used to link index client survey responses with returned self-test kits.

The number of partners and the number of kits provided will be documented by study staff. Each self-test kit will be in a package that also contains a referral card. The referral card can be used for (1) those who test HIV-positive and need to present for confirmatory testing and link to care, (2) those who do not want to use the self-test kit and would rather test with an HDA, or (3) clients who experience difficulty or discomfort with the self-test kit and choose to test at a facility. The referral card will include information about the fa-

cility, including a map. The card will also contain a notation that if it is returned to another facility, the facility should contact the study team so that the card can be collected and recorded as “returned”. Study staff will periodically visit nearby testing sites to determine if any referral cards have been returned to those sites.

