3.3.1. Description of Randomization and Study Arms

Randomization from Aim 1 will be accomplished such that facilities randomized to the self-test intervention in Aim 1 will be self-test intervention sites for Aim 2 and sites randomized to standard of care and optimized standard of care for Aim 1 will continue as standard of care and optimized standard of care sites for Aim 2.

Description of Study Arms

1. **Standard of care arm:** Facilities randomized to the standard of care arm will use MOH approved referral mechanisms, without any intervention from the study team. Standard of care quality will vary by facility and may include some level of partner referral services for index partners such as referral slips. Referral slips may be given at HIV testing or ART clinics. Sites will be asked to counsel clients to have their partners bring referral slips back to the clinic to document the number of partners presenting for HIV testing. A random subset of HIV-positive clients in the standard of care arm will complete an anonymous survey to answer questions about whether they used referral slips and whether they know if partners came to a health facility for testing.

2. **Optimized standard of care arm:** Facilities randomized to optimized standard of care will be supported by the study team to systematically perform referral services following Ministry of Health Guidelines. Providers will receive an initial refresher training on partner testing followed by regular mentoring visits. Job aids will also be used to remind providers about the importance of partner testing. Standard of care procedures involve counseling HIV-positive individuals about the importance of partner testing and providing ‘referral slips’ to the index client to distribute to every sexual partner within the prior 12 months. Referral slips will be used to encourage partners to come to the facility for HIV testing. Sites will be asked to counsel clients to have their partners bring referral slips back to the clinic to document the number of partners presenting for HIV testing. A random subset of participants in the optimized standard of care arm will complete an anonymous survey to answer questions about whether they used referral slips and whether they know if partners came to a health facility for testing.

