3.4.1.2 Baseline Visit for Index Client

A random sample of individuals will be screened and consented as they exit their ART visit. This will include ART clients who report having a sexual partner with an unknown HIV status. After written informed consent has been obtained, study staff will collect basic socio-demographics (including age, gender, marital status, and number of partners), HIV characteristics (date of HIV diagnosis, whether on ART and date started), and the number of eligible sexual partners who qualify for index testing referral slips. Individuals will also be asked whether they were offered a referral slip on the day of the survey.

Follow-up Visit of Index Clients

All index clients will be seen by study staff when they come for their next ART follow-up visit. A brief survey will be performed to collect information about whether the client disclosed their HIV status to their sex partner(s), whether they gave referral slips to their partner(s), and knowledge about whether partners completed a test, knowledge of their partner's test result, and knowledge about their partner's linkage to care. We will also survey the index client to determine whether any gender-based violence or fear of gender-based violence resulted from use of the self-tests. Index clients who do not return for their ART follow-up visit (more than two weeks late) will be traced through standard site protocols and surveyed either in the community or at the facility, if they return to care.

HIV testing registers will also be reviewed to measure the number of individuals tested through partner referrals and the proportion of partner referral tests who were identified as HIV-positive. All registry data will be anonymized. Records from partner notification clients aged 15 years and older will be included in the study. For those who are HIV-positive, the HTC and ART registers will be reviewed to determine if the patient started ART and presented for their four-week follow-up visit.

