3.4.4.3 Follow-up of Partner Self-Testing

The number of index partners tested will be determined based on the number of self-test kits returned to village and health facility lockboxes and triangulated with self-reports from a follow-up survey with the index client. Additionally, partners with a positive self-test kit who present to the facility for confirmatory testing and linkage to care, and/or partners who did not use the self-test kit but present to the facility for HIV testing will be accounted for through the returned referral cards. Like self-test kits, referral cards will be identified with a unique code, allowing the partner to be linked to the index client.

For those who are HIV-positive and present to the clinic for care, the ART register will be reviewed four weeks later to determine if the patient starts ART and presents for their four-week follow-up visit. All data from registers will be anonymized for use by the study team. In addition, index clients will provide self-reports about partner linkage to ART during a follow-up survey.

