5. STATISTICAL METHODS

5.1. Outcome Measures

3.5.1.1 Sample Size and Statistical Analysis for Primary Outcome Measures

We will have 15 clusters (facilities) available for randomization, and therefore, estimated our sample size assuming a fixed number of clusters (k) and an equal number of clusters per arm. We also assumed an equal number of participants per cluster. The below calculations were determined using a minimum sample size. Assuming a type I error of 0.05, an intracluster correlation of 0.004 and sample sizes of 600 HIV-positive patients per arm, we have 89% power to detect a difference in testing coverage of 20% in study arm 2 (optimized standard of care) and 40% in study arm 3 (self-testing). Because we are uncertain about the proportion of partners who will test under each arm, we have considered a range of possibilities, with the majority of scenarios providing at least 87% power to detect a difference between the two arms of interest (optimized standard of care and self-testing) (Figure 4).

We will calculate descriptive statistics, including mean/median, variation (standard deviation, kurtosis), range, and frequency distributions for the demographic and clinical characteristics, overall and by study arm. The outcomes of interest include the proportion of partners tested and HIV-positivity of partners. Differences in the prevalence of each of the outcomes of interest will be examined by study arm as well as by other factors of interest including demographic characteristics (e.g., age, gender), clinical characteristics (e.g., reason for clinic visit), and structural factors (e.g., geographic location). The differences will be evaluated using t-tests, Mann-Whitney U test (or other non-parametric tests), chi-square methods, and Fisher's exact test as appropriate. In order to assess factors associated with partner's HIV testing/positivity, we will use hierarchical linear models in order to account for clustering of effects within each clinic. Separate models will be developed for each outcome of interest and covariates of interest include patient characteristics (e.g., age, gender) and other structural and contextual factors.

Qualitative Analysis for Secondary Outcome Measures

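### The Aim 2 proportion of partners tested has no stated denominator, and both the eligible-partner counts and the sources for partners tested differ by arm

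*Combined protocol and SAP*

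**What the plan says.** The Aim 2 statistical section (3.5.1.1) and the Aim 2 cost-effectiveness section (6.2) name the outcome as the proportion of partners tested. Neither says which partners form the denominator. The primary objective in 3.1.1 is worded as a greater number of partners tested.

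The baseline partner counts are described by arm:

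- Standard and optimized standard of care (3.4.1.2 and, in the same words, 3.4.2.2): "the number of eligible sexual partners who qualify for index testing referral slips".
- Self-testing (3.4.4.1): "the number of eligible sexual partners they plan to give self-test kits". Kits go to catchment-area partners "for whom the index client is willing to provide the test kit (up to three sexual partners").
- All three arms also collect the number of partners among the socio-demographic items. Section 3.4.4.1 adds that staff document the number of partners and the number of kits. Neither item is stated to be the eligible count.

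For the optimized arm, 3.3.1 describes slips for the client "to distribute to every sexual partner within the prior 12 months"; 4.2.1 narrows this to partners of unknown status or who tested negative more than 6 months ago.

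For the numerator in the self-testing arm, 3.4.4.3 says: "The number of index partners tested will be determined based on the number of self-test kits returned to village and health facility lockboxes". These counts are triangulated with index-client report, and returned referral cards are added. Section 3.4.4.1 also says: "Index clients will also be given self-test kits for themselves if they wish to use them to complete couples counseling". The comparator arms rely on index-client report and anonymized testing registers (follow-up text under 4.1 and 4.2).

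**The concern.** How many partners are handed a kit or a slip is part of each intervention. Who is counted in the outcome is not, and that must be the same in every arm for the proportions to be comparable. A partner whom the client does not intend to approach is plausibly among the least likely to test. Under the comparator wording that partner is counted; under the self-testing wording that partner can be left out. The filter acts after randomization and in one arm only.

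The self-testing arm also has its own stated source for partners tested, the returned kits. A proportion built from arm-specific counts above and below the line could show a difference that is partly a matter of counting. Analysis may not be able to repair this later: an eligible partner who was never listed cannot be added, and an unmarked kit cannot be assigned to the person who used it.

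**Working it through.** **1. The plan's own figure.** Inputs from 3.5.1.1: "Assuming a type I error of 0.05, an intracluster correlation of 0.004 and sample sizes of 600 HIV-positive patients per arm, we have 89% power" for 20% against 40%, with 15 clusters split equally, so 5 clusters per arm and 600/5 = 120 clients per cluster. The unit is the index client, not the partner.

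- Design effect = 1 + (120 − 1) × 0.004 = 1.476; effective n = 600/1.476 = 406.5 per arm.
- Power = Φ{[d − 1.96·√(2p̄(1−p̄)/n)] / √([p1(1−p1) + p2(1−p2)]/n)}, with d = 0.20 and p̄ = 0.30. Result: above 99.9%, not 89%.
- An intracluster correlation of 0.04 gives a design effect of 5.76, effective n of 104.2 and power of 88.9%. That matches the printed 89%, but the documents do not say it was used. This is a separate matter; it is the reason both values are carried below.

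**2. The baseline counts side by side.**

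| | Comparator arms | Self-testing arm |
|---|---|---|
| Eligible-partner count | Partners who qualify for a slip | Partners the client plans to give a kit |
| Client willingness limit on kit or slip | None stated | Yes |
| Cap on kits or slips | None stated | Three |
| General number of partners | Recorded, not stated to be eligible partners | Recorded, not stated to be eligible partners |

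**3. What follows if the eligible counts are the denominators.** Let w be the share of eligible self-testing-arm partners on the plan-to-give list. The documents do not give w, so 0.95 to 0.70 is an assumed range. Let q be the coverage of partners off the list. With true coverage of 20% among all eligible partners in both arms, coverage on the list is [0.20 − (1 − w)q]/w. If q = 20%, the list shows 20% and there is no bias. If q = 0, it shows 0.20/w, as tabulated. Values of q in between give smaller gains.

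The last two columns give the chance of declaring self-testing superior when the arms do not differ (nominal 2.5% in that direction). They use the formula above with p1 = 0.20 and p2 = 0.20/w, and assume one partner per client.

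| w | Shown coverage | Spurious gain (points) | Chance, ICC 0.004 | Chance, ICC 0.04 |
|---|---|---|---|---|
| 0.95 | 21.1% | 1.1 | 5.6% | 3.8% |
| 0.90 | 22.2% | 2.2 | 11.8% | 5.8% |
| 0.80 | 25.0% | 5.0 | 40.0% | 13.6% |
| 0.70 | 28.6% | 8.6 | 81.4% | 30.2% |

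**4. The numerator.** Three features differ by arm, and they do not all point the same way.

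- An index client may hold a kit for personal use. Kits carry an ID linked to the index client (3.4.4.1), and no mark is described that tells an index kit from a partner kit. A returned index kit could raise the self-testing count.
- A used partner kit that is never returned lowers it.
- Comparator registers count people tested through partner referral and are anonymized. They may include partners of clients who were never enrolled, which raises the comparator count.

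**The case against.** The strongest reply is that no section names either baseline count as the denominator. The objective is a number of partners, every arm also records a general number of partners, and the willingness and three-kit limits govern distribution, not the outcome. On this view the plan has a gap and no demonstrated bias.

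Much of that stands, and it rules out several stronger readings that a reader might infer:

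- *The primary contrast is biased.* The documents leave the denominator open, so this is a risk that depends on a choice not yet stated.
- *The self-testing arm records only plan-to-give partners.* It also records a number of partners, though not stated to be the eligible ones.
- *The catchment limit is peculiar to self-testing.* Section 3.2.1 requires an eligible catchment-area partner in all arms, and 3.3.2 screens for one in the comparator arms.
- *Part of the planned 20-point difference is artefact.* If 10% to 30% of partners were off the list and untested, 40% would correspond to 36% to 28% of all eligible partners (40% × 0.90 to 40% × 0.70), a gap of 4 to 12 points. That reads the planned 40% as coverage among plan-to-give partners, which 3.5.1.1 does not say.
- *Index clients' own kits swell the count by a known amount.* No return rate is given, these kits are optional, the lockbox instructions in 3.3.1 and 3.4.4.2 are addressed to partners, and triangulation may catch some.
- *Both differences favour self-testing.* The net direction of the numerator difference is not shown.

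The reply does not dispose of the point. The only counts expressly limited to eligible partners follow different rules by arm, and no rule says which source prevails when kits and client report disagree. Wording the objective as a number avoids the denominator problem but not the difference in how tests are found.

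**Conclusion.** The point holds as a defect of definition with a foreseeable direction for the denominator. The Aim 2 proportion has no stated denominator, and the eligible-partner counts the plan provides are not comparable across arms. Using them would favour self-testing to the extent that partners off the plan-to-give list test less often than those on it.

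The size cannot be derived from the documents. The illustrated gain of 1.1 to 8.6 points assumes w from 0.95 to 0.70, true coverage of 20% in both arms and no testing off the list; the error rates further assume one partner per client. The numerator difference is real, with uncertain net direction. Both should be settled before data collection.

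**What to change.** - In every arm, before any question about willingness and before arm-specific counselling, list the same partners under one definition: sex partner in the past 12 months, unknown status as defined in 3.2.1, living in the catchment area, with no cap on the list. Name this list in 3.5.1.1 as the denominator. This does not alter how many kits or slips are given.
- Keep planned and distributed kits as process measures.
- Mark each kit as index or partner, and count only partner kits.
- Base the arm contrast on index-client report at the follow-up visit, which all three arms collect, with kits, cards and registers as supporting data. Sections 3.3.1 and 3.3.2 call the comparator survey anonymous, while 4.1 and 4.2 describe following the same clients up, so state how the baseline list is linked to the follow-up report.

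The cost is case report form and protocol wording and a label on the kits. The drawbacks are that index-client report is unblinded and second-hand, and that self-testing coverage may look less favourable. Showing the supporting sources beside it lets a reader judge the first.

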4.2. Optimized Standard of Care Arm

4.2.1. Partner Notification and Referral

The study team will provide trainings, job aids, and regular mentorship to promote optimized standard of care in regards to partner notification and referral strategies for HIV-positive clients with partners who have an unknown HIV status. Under optimized standard of care, providers will ask clients at every ART visit whether they have current or recent (within 12 months) sex partners with unknown HIV status or tested negative for HIV more than 6 months ago. Clients will be counseled on the importance of partner notification and testing and given a partner notification slip to assist in partner notification and testing referral. Individuals will be counseled to ask their partners to return the referral slips when they come for testing. Partners who present at the facility for HIV testing will be tested in private rooms by trained HDAs following Ministry of Health guidelines. HDAs will ask all clients presenting for testing whether they were referred by a partner and this will be indicated in a column in the HIV testing register. Serial HIV testing will be performed with Determine and Uni-Gold as per standard of care. Those that test positive will be counseled and referred to ART services. ART initiation will follow standard clinic protocols under the universal treatment (Test and Treat policy).

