3.4.2.2 Baseline Visit for Index Client

A random sample of individuals will be screened and consented as they exit their ART visit. This will include ART clients who report having a sexual partner with an unknown HIV status. After written informed consent has been obtained, study staff will collect basic socio-demographics (including age, gender, marital status, and number of partners), HIV characteristics (date of HIV diagnosis, whether on ART and date started), and the number of eligible sexual partners who qualify for index testing referral slips. Individuals who consent will also be asked whether they were offered a referral slip on the day of the survey.

Follow-up Visit of Index Clients

All index clients will be seen by study staff when they come for their next ART follow-up visit. A brief survey will be performed to collect information about whether the client disclosed their HIV status to their sex partner(s), whether they gave referral slips to their partner(s), and knowledge about whether partners completed a test, knowledge of their partner's test result, and knowledge about their partner's linkage to care. We will also survey the index client to determine whether any gender-based violence or fear of gender-based violence resulted from use of the self-tests. Index clients who do not return for their ART follow-up visit (more than two weeks late) will be traced through standard site protocols and surveyed either in the community or at the facility, if they return to care.

HIV testing registers will also be reviewed to measure the number of individuals tested through partner referrals and the proportion of partner referral tests who were identified as HIV-positive. All registry data will be anonymized. Records from partner notification clients aged 15 years and older will be included in the study. For those who are HIV-positive, the ART register will be reviewed to determine if the patient started ART and presented for their four-week follow-up visit.

At the time of follow-up, a random sample of 40 index clients (20 men and 20 women) will be selected and asked to participate in semi-structured, in-depth interviews to explore the feasibility and acceptability of providing referral slips to partners, including challenges with disclosure and questions around harm or perceived risk of harm due to distributing the referral slip.

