3.4.4.4 Follow-up Visit of Index Clients

All index clients will be seen by study staff when they come for their next ART follow-up visit. A brief survey will be performed to collect information about whether the client disclosed their HIV status to their sex partner(s), whether they gave self-test kits to their partner(s), and knowledge about whether partners completed the test, knowledge of their partner’s test result, and knowledge about their partner’s linkage to care. We will also survey the index client to determine whether they were able to successfully show their partner(s) how to use the kit and whether any gender-based violence or fear of gender-based violence resulted from use of the self-tests. Index clients who do not return for their ART follow-up visit (more than two weeks late) will be traced through standard site protocols and surveyed either in the community or at the facility, if they return to care.

A random sample of 40 index clients (20 men and 20 women) and 40 index partners (20 men and 20 women) will be selected and asked to participate in semi-structured, in-depth interviews to explore the feasibility and acceptability of providing self-test kits to partners, including challenges with disclosure and questions around harm or perceived risk of harm due to distributing the kits.

2.4.4.5 *Follow-up Visits with Index Partners*

Index partners will be recruited for in-depth interviews through index clients (n=40). During follow-up visits with index clients, a random subset of clients will be given a study invitation card to be given to their sexual partner who was given a self-test kit. The study invitation card will describe the in-depth interview they are being recruited for and provide a study-specific phone number the index partner can call in order to participate in the study. In addition, index clients will be asked if the study team could call the randomly selected partner to discuss the study. Index clients will be told the purpose of the call. If index clients give permission to contact the index partner, up to 2 phone numbers will be collected. Index partners will be called up to 3 times over a 2-week period for recruitment into the study. If the index partner cannot be reached after the third try, the partner will be listed as “unreachable” and excluded from the study.

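### Aim 2 counts eligible partners differently by arm and designates no common denominator or test source for the proportion of partners tested

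*Combined protocol and SAP*

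**What the plan says.** All references are to Aim 2 of the combined protocol and SAP.

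**Outcome.** The primary objective (section 3.1.1) concerns the number of partners tested, kits against optimized referral slips. Section 3.5.1.1 turns this into a proportion of partners tested, with no denominator and no data source.

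**Baseline partner count.** In the optimized arm (3.4.2.2), and in the same terms in the standard arm (3.4.1.2), staff record "the number of eligible sexual partners who qualify for index testing referral slips". In the self-testing arm (3.4.4.1) the matching item is "the number of eligible sexual partners they plan to give self-test kits". All three baseline visits also list a general number of partners among the socio-demographic items. Section 3.4.4.1 adds that "The number of partners and the number of kits provided will be documented by study staff", without saying which partners.

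**Tests, optimized arm.** The follow-up survey asks index clients for "knowledge about whether partners completed a test". In addition, "HIV testing registers will also be reviewed to measure the number of individuals tested through partner referrals", and "Records from partner notification clients aged 15 years and older will be included in the study". Under section 4.2.1, "HDAs will ask all clients presenting for testing whether they were referred by a partner and this will be indicated in a column" of the testing register. Register data are anonymized.

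**Tests, self-testing arm.** Section 3.4.4.3 bases the number tested on returned kits, triangulated with the index client's survey, and adds returned referral cards. Kits and cards carry codes linked to the index client. The survey (3.4.4.4) asks for "knowledge about whether partners completed the test".

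**The concern.** A proportion of partners tested compares arms fairly only if the same kind of partner enters the denominator in each arm and the same kind of test enters the numerator. Here an eligible partner whom the client does not intend to approach is counted in the standard of care arms but can be absent from the self-testing arm's count. Partners a client will not approach are plausibly less likely to test, so leaving them out would raise that arm's proportion. On the numerator side, a register tally may include partners of clients who never enrolled, while kit returns may miss tests that took place.

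At stake is the primary contrast of Aim 2. Two analysts could both follow the plan and compute different results. If the self-testing arm never records its eligible partners on the same terms, that count cannot be rebuilt reliably afterwards.

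**Working it through.** **1. The plan's own figures.** Section 3.5.1.1 assumes coverage of 20% (optimized) and 40% (self-testing), 600 HIV-positive patients per arm, 5 clusters per arm (120 per cluster), ICC 0.004, and states 89% power. The design effect is 1 + 119 × 0.004 = 1.476, so the effective size is 600 / 1.476 = 406.5 per arm and two-sided power exceeds 99.9%. With ICC 0.04 the design effect is 5.76, the effective size 104.2 and power 88.9%. The stated power is therefore not reproduced at the stated ICC. That is a separate matter; only the 20% and 40% are used below.

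**2. Denominator items side by side.**

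| Item | Optimized arm | Self-testing arm |
|---|---|---|
| Specific baseline count | Eligible partners qualifying for slips | Eligible partners the client plans to give kits |
| General number of partners | Collected, not limited to eligible partners | Collected, not limited to eligible partners |
| Further count | None described | Number of partners and of kits, partners undefined |
| Limits on slips or kits | No catchment limit, willingness condition or cap stated (3.3.1, 4.2.1) | Catchment, willingness, at most three (3.4.4.1) |

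Section 3.4.4.1 itself treats eligibility and willingness as separate conditions for giving a kit, so the two specific counts need not agree. No row is named as the denominator.

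**3. Numerator items side by side.** In the optimized arm, providers ask clients at every ART visit and give slips (4.2.1), while enrolled clients are a random sample (3.4.2.2). The register can therefore hold partners of non-enrolled clients, and no link to enrolled clients is described. In the self-testing arm, returns are linked to enrolled clients by code. The one item present in all arms is the survey question on whether partners tested, but 3.4.4.3 gives it a triangulating role and section 4.2 gives it no stated rank against the register.

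**4. Illustration of the denominator.** Assume 40% is true coverage of all eligible partners of enrolled clients. Let *w* be the share of eligible partners the client plans to give a kit and *u* the testing rate among the rest. Neither is in the documents. If planned kits were the denominator, and only tests among those partners were counted, the self-testing arm would read (0.40 − (1 − *w*)*u*) / *w*:

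- *w* = 1: 40.0%, difference from 20% is 20.0 points (no change).
- *w* = 0.95, *u* = 0.20: (0.40 − 0.01) / 0.95 = 41.1%, difference 21.1 points.
- *w* = 0.90, *u* = 0.10: (0.40 − 0.01) / 0.90 = 43.3%, difference 23.3 points.
- *w* = 0.80, *u* = 0: 0.40 / 0.80 = 50.0%, difference 30.0 points.

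**5. Illustration in the other direction.** If only returned kits were counted and 80% or 70% of used kits came back (also assumed), 40% would read as 0.40 × 0.80 = 32% or 0.40 × 0.70 = 28%. Survey triangulation may correct this, but no rule says how.

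**The case against.** The best defence is that this is a gap in specification, with usable data already collected. Every arm records a number of partners, every arm asks at follow-up whether partners tested, and one partner-status and catchment criterion (3.2.1) governs enrolment throughout. In the self-testing arm, listing partners separately from kits suggests a count that is not simply kits handed out. Much of this stands: a common analysis is feasible. What remains is that the general item is not confined to eligible partners, the further count is undefined, and the survey is not designated as the primary source.

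The sample size is also expressed in index patients. If coverage is meant per index client, the denominator illustration does not apply.

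A reader might infer that the plan divides the self-testing arm by planned kits and so favours self-testing. Nothing in the documents makes that count the denominator. A reader might also infer that the optimized arm's register total will be divided by enrolled clients' partners, inflating that arm and shrinking the effect. No section proposes that ratio, so no size is attached to it here.

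Limits on who receives a kit belong to the strategy under test and are not criticised.

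Finally, relying on the survey is debatable. A client who demonstrates and hands over a kit may know better whether the partner tested than one who hands over a slip. That objection stands as a cost of the remedy.

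**Conclusion.** The point holds in this limited form: eligible partners are recorded on different terms by arm, and neither a common denominator nor a common test source is designated for the Aim 2 primary contrast, although items that could serve are collected in all arms. The change should be made, because the self-testing arm otherwise lacks a clearly comparable count of eligible partners.

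The documents do not show that the comparison is biased in a given direction. A planned-kit denominator would raise the self-testing arm, counting only returned kits would lower it, and an unlinked register count could overstate the optimized arm. The figures of 41.1% to 50% and of 28% to 32% rest on assumed shares and on reading coverage as a proportion of eligible partners. They show sensitivity and are not estimates.

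**What to change.** - **Denominator.** In every arm, ask the same baseline question: how many sexual partners in the past 12 months live in the catchment and have never tested or last tested negative more than 6 months ago. In the self-testing arm, ask it before kits are handed out. Use the answer as the denominator whether or not a slip or kit was given, and keep planned kits as a process measure.
- **Numerator.** Count only partners of enrolled index clients. Report the survey-based contrast, which is available in all arms, with kit and card returns and register referrals as supporting or sensitivity measures. In the self-testing arm, report agreement between survey and coded returns. Do not divide unlinked register totals by enrolled clients' partners.
- **Kits for index clients.** Clients may also receive kits for themselves, and all kits carry an ID linked to the client. Make sure the ID separates these from partner kits.

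**Cost.** Protocol wording and a few survey items; the two standard of care arms already ask for an eligible-partner count. The downsides are:

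- more weight on self-report in an unblinded trial in which self-testing participants are reimbursed (7.4);
- possibly better knowledge of partner testing among clients who give kits;
- some risk that a more explicit question prompts clients in the standard of care arms, whose consent (under 3.3.2) avoids detail on the outcome for that reason.

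One conflict must be settled first. Sections 3.3.1 and 3.3.2 describe an anonymous survey in the standard of care arms, whereas 3.4.1.2 and 3.4.2.2 describe written consent and a follow-up visit. A baseline denominator per client needs linked follow-up.
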